8.1.10. Columbia Suicide Severity Rating Scale – Children’s’ (Baseline and Since Last Visit)

Descriptive statistics (count, percentage of yes/no responses) will be provided for each item of the C-SSRS that is completed at each time point. Note that if a patient answers “No” to question “1” or question “2”, then the patient will not be asked to answer question “4” or question “5”.

8.1.11. AED Medications

The following data will be summarized separately for each AED medication:

- Plasma concentration occurring at Day 1
- Elapse time between last AED dose and the time of plasma sample collection.

Descriptive statistics (arithmetic mean, median, SD, minimum, maximum, coefficient of variation, geometric mean [plasma concentration]) for the AED plasma trough concentrations and elapse time will be presented at each nominal PK sampling time: screening, pre-dose on study Visit 3/Week 6, Visit 4/Week 14, and Visit 7/Week 38 EOS/ET Visits.

8.1.12. CBD and THC Plasma Levels

The following PK parameters for CBD will be calculated/derived from the data. Plasma PK will be calculated on trough:

- Steady-state plasma concentration occurring just prior to the next dose of ZYN002.
- Elapsed time between the last ZYN002 dose and time of plasma sample collection.

Descriptive statistics (arithmetic mean, median, SD, minimum, maximum, coefficient of variation, geometric mean [plasma concentration]) for the plasma trough concentrations and elapsed time will be presented for all patients combined at each nominal blood sampling time (pre-dose Weeks 6, 14, 38, and ET).

Exploratory analyses on the effect of CBD on plasma levels of AEDs, or vice versa, may be explored. Analyses for CBD metabolites are exploratory and may be conducted. CBD and THC plasma levels will be summarized at each visit using descriptive statistics.

9. STATISTICAL SOFTWARE

All data listings, summaries, and statistical analyses will be generated using SAS[®] Version 9 or higher. All data collected on the electronic case report form (eCRF) will be listed.

10. CHANGES FROM THE PROTOCOL

None identified.

11. LIST OF SUMMARIES AND LISTINGS

Summary Number	Title	Population	Period 1 Display
14.1.1	Summary of Patient Disposition	Enrolled	X
14.1.2	Summary of Demographics	Safety Analysis Set	X
14.1.3	Summary of Baseline Characteristics	Safety Analysis Set	X
14.1.4	Summary of Medical History	Safety Analysis Set	X
14.1.5	Summary of Prior Medications by Therapeutic Class and Preferred Term	Safety Analysis Set	X
14.1.6	Summary of Electrocardiogram Findings at Baseline	Safety Analysis Set	X
14.1.7	Summary of Physical Examination Findings at Baseline	Safety Analysis Set	X
14.1.8	Summary of Neurological Examination Findings at Baseline	Safety Analysis Set	X
14.2.1	Summary of Change from Baseline to Weeks 6, 14, 22, 30, and 38 in the ABC-C Checklist	mITT Analysis Set	X
14.2.2	Summary of 25% and 50% responders at Weeks 6, 14, 22, 30, and 38 in the ABC-C Checklist	mITT Analysis Set	X
14.2.3	Summary of Change from Baseline to Weeks 6, 14, 22, 30, and 38 in the ADAMS Checklist	mITT Analysis Set	X
14.2.4	Summary of Change from Baseline to Weeks 6, 14, 22, 30, and 38 in the CGI-S Scale	mITT Analysis Set	X
14.2.5.1	Summary of CGI-I at Baseline, Weeks 6, 14, 22, 30, and 38	mITT Analysis Set	X
14.2.5.2	Shifts from Baseline to Weeks 6, 14, 22, 30, and 38 in CGI-I	mITT Analysis Set	X
14.2.6.1	Summary of Change from Baseline to Weeks 6, 14, 22, 30, and 38 in the PARs-R Scale	mITT Analysis Set	X
14.2.6.2	Summary of Shifts from Baseline to Weeks 6, 14, 22, 30, and 38 in CGI –I Categories (≤ 52 and > 52)	mITT Analysis Set	X
14.3.1.1.1	Summary of Sachet Information (Period 1)	Safety Analysis Set	X
14.3.1.1.2	Summary of Study Drug Duration (Period 1)	Safety Analysis Set	X
14.3.1.2.1	Summary of Sachet Information (Period 2)	Safety Analysis Set	
14.3.1.2.2	Summary of Study Drug Duration (Period 2)	Safety Analysis Set	
14.3.1.3.1	Summary of Sachet Information (Overall)	Safety Analysis Set	
14.3.1.3.2	Summary of Study Drug Duration (Overall)	Safety Analysis Set	
14.3.2.1.1	Overall Summary of Treatment Emergent Adverse Events (Period 1)	Safety Analysis Set	X
14.3.2.1.2	Overall Summary of Treatment Emergent Adverse Events (Period 2)	Safety Analysis Set	
14.3.2.1.3	Overall Summary of Treatment Emergent Adverse Events (Overall)	Safety Analysis Set	
14.3.2.2.1	Summary of Treatment Emergent Adverse Events by System Organ Class, and Preferred Term (Period 1)	Safety Analysis Set	X
14.3.2.2.2	Summary of Treatment Emergent Adverse Events by System Organ Class, and Preferred Term (Period 2)	Safety Analysis Set	
14.3.2.2.3	Summary of Treatment Emergent Adverse Events by System Organ Class, and Preferred Term (Overall)	Safety Analysis Set	
14.3.2.3.1.1	Summary of Treatment Emergent Adverse Events by System Organ Class, Preferred Term, and Severity (Period 1)	Safety Analysis Set	X
14.3.2.3.1.2	Summary of Treatment Emergent Adverse Events by System Organ Class, Preferred Term and Severity Including All Events by Treatment Group (Period 1)	Safety Analysis Set	X

Summary Number	Title	Population	Period 1 Display
14.3.2.3.2.1	Summary of Treatment Emergent Adverse Events by System Organ Class, Preferred Term, and Severity (Period 2)	Safety Analysis Set	
14.3.2.3.2.2	Summary of Treatment Emergent Adverse Events by System Organ Class, Preferred Term and Severity Including All Events by Treatment Group (Period 2)	Safety Analysis Set	
14.3.2.3.3.1	Summary of Treatment Emergent Adverse Events by System Organ Class, Preferred Term, and Severity (Overall)	Safety Analysis Set	
14.3.2.3.3.2	Summary of Treatment Emergent Adverse Events by System Organ Class, Preferred Term and Severity Including All Events by Treatment Group (Overall)	Safety Analysis Set	
14.3.2.4.1	Summary of Related Treatment Emergent Adverse Events by System Organ Class, Preferred Term (Period 1)	Safety Analysis Set	X
14.3.2.4.2	Summary of Related Treatment Emergent Adverse Events by System Organ Class, Preferred Term (Period 2)	Safety Analysis Set	
14.3.2.4.3	Summary of Related Treatment Emergent Adverse Events by System Organ Class, Preferred Term (Overall)	Safety Analysis Set	
14.3.2.5.1	Summary of Related Treatment Emergent Adverse Events by System Organ Class, Preferred Term, and Severity (Period 1)	Safety Analysis Set	X
14.3.2.5.2	Summary of Related Treatment Emergent Adverse Events by System Organ Class, Preferred Term, and Severity (Period 2)	Safety Analysis Set	
14.3.2.5.3	Summary of Related Treatment Emergent Adverse Events by System Organ Class, Preferred Term, and Severity (Overall)	Safety Analysis Set	
14.3.2.6.1	Summary of Serious Adverse Events by System Organ Class, Preferred Term (Period 1)	Safety Analysis Set	X
14.3.2.6.2	Summary of Serious Adverse Events by System Organ Class, Preferred Term (Period 2)	Safety Analysis Set	
14.3.2.6.3	Summary of Serious Adverse Events by System Organ Class, Preferred Term (Overall)	Safety Analysis Set	
14.3.2.7.1	Summary of Adverse Events Leading to Treatment Discontinuation by System Organ Class, Preferred Term (Period 1)	Safety Analysis Set	X
14.3.2.7.2	Summary of Adverse Events Leading to Treatment Discontinuation by System Organ Class, Preferred Term (Period 2)	Safety Analysis Set	
14.3.2.7.3	Summary of Adverse Events Leading to Treatment Discontinuation by System Organ Class, Preferred Term (Overall)	Safety Analysis Set	
14.3.2.8.1	Summary of Fatal Adverse Events by System Organ Class, Preferred Term (Period 1)	Safety Analysis Set	X
14.3.2.8.2	Summary of Fatal Adverse Events by System Organ Class, Preferred Term (Period 2)	Safety Analysis Set	
14.3.2.8.3	Summary of Fatal Adverse Events by System Organ Class, Preferred Term (Overall)	Safety Analysis Set	
14.3.2.9.1	Summary of Treatment Emergent Adverse Events by Preferred Term in Descending Order of Frequency (Period 1)	Safety Analysis Set	X
14.3.2.9.2	Summary of Treatment Emergent Adverse Events by Preferred Term in Descending Order of Frequency (Period 2)	Safety Analysis Set	
14.3.2.9.3	Summary of Treatment Emergent Adverse Events by Preferred Term in Descending Order of Frequency (Overall)	Safety Analysis Set	
14.3.3	Summary of Vital Signs by Visit	Safety Analysis Set	X
14.3.4.1	Summary of Electrocardiogram by Visit	Safety Analysis Set	X
14.3.4.2	Summary of Shifts from Baseline to Each Visit in Electrocardiogram Findings	Safety Analysis Set	X
14.3.5.1	Summary of Shifts from Baseline to each Visit in Physical Exam Findings	Safety Analysis Set	X

Summary Tables, continued

Summary Number	Title	Population	Period 1 Display
14.3.5.2	Summary of Shifts from Baseline to each Visit in Neurological Exam Findings	Safety Analysis Set	X
14.3.5.3	Summary of Shifts from Baseline to each Visit in Chemistry and Hematology	Safety Analysis Set	X
14.3.6.1.1	Summary of Chemistry Laboratory Results and Changes from Baseline to Each Visit	Safety Analysis Set	X
14.3.6.1.2	Summary of Clinically Significant Chemistry Laboratory Values	Safety Analysis Set	X
14.3.6.2.1	Summary of Hematology Laboratory Results and Changes from Baseline to Each Visit	Safety Analysis Set	X
14.3.6.2.2	Summary of Clinically Significant Hematology Laboratory Values	Safety Analysis Set	X
14.3.6.3	Summary of Urinalysis Laboratory Values	Safety Analysis Set	X
14.3.6.4	Summary of Testosterone Laboratory Values	Safety Analysis Set	X
14.3.7	Summary of Concomitant Medications by Therapeutic Class and Preferred Term	Safety Analysis Set	X
14.3.8.1	Summary of Patient Monthly Skin Irritation Scores	Safety Analysis Set	
14.3.8.2	Summary of Investigators Skin Irritation Scores at Each Visit	Safety Analysis Set	
14.3.9	Summary of Columbia Suicide Severity Rating Scale Children's Version Positive Ratings	Safety Analysis Set	
14.3.10	Summary of Trough Plasma Concentrations for Anti-Epileptic Drugs at each Sampling Time (Weeks 6, 14, and 38)	PK Analysis Set	
14.3.11	Summary of CBD and THC Plasma Levels at Each Visit by Dose	Safety Analysis Set	

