7.6.20. Blood Samples for Valproic Acid

At Screening, Week 6, Week 14, and Week 38 EOS/ET Visits, patients will have blood drawn for plasma level of their valproic acid (for patients receiving valproate or valproic acid).

All effort should be made to obtain a trough sample for the valproate/valproic acid. AED name, time taken, and amount and date of the last dose will be captured before the blood samples are collected. At each monthly visit, the Investigator will review the valproic acid (for patients receiving valproate or valproic acid) level and the dose of concomitant AEDs in the event they require adjusting if the patient experiences AEs that warrant a dose change.

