12. PHARMACOKINETIC ASSESSMENTS

12.1. Blood Sample Collection

A 2-3 -mL blood sample (trough) for PK analysis of CBD/THC will be collected into sodium heparin tubes at Screening, pre-dose on study Visit 3/Week 6, Visit 4/Week 14, and Visit 7/Week 38 EOS/ET Visits.

In addition, a separate blood sample for valproic acid levels (for patients taking valproate or valproic acid for treatment of seizures or epilepsy) will be collected at Screening, Week 6, 14, and Week 38 EOS/ET Visits. Valproic acid samples will be analyzed by a local laboratory. For patients receiving valproate/valproic acid medication and having a Taper Period their final blood draw for PK and valproic acid levels will be taken at Week 38.

PK blood samples for CBD/THC analysis will be placed on ice until centrifuged. The blood samples will be placed in a refrigerated centrifuge within 60 minutes of collection and spun at high speed (2500 revolutions per minute) for 10 minutes at 4°C. Plasma samples will be split in half and transferred into standard polypropylene cryovial tubes for the plasma aliquots. The plasma samples will be frozen at a freezer temperature of -80°C or below (± 10 C), within two hours after collection and will remain frozen until shipped. Half of the plasma sample will be retained at the investigative site as a back-up sample. Half of the frozen samples will be packed in dry ice sufficient to last the number of days applicable to transport. Plasma samples will be shipped to a lab chosen by the Sponsor.

An inventory of the samples shipped will accompany the package.

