- c. Vital signs (including blood pressure, heart rate, respiratory rate, and infrared forehead or oral or tympanic temperature) will be recorded after the patient has been sitting for at least 5 minutes. Vital signs will be assessed at each study visit pre-dose.
- d. One ECG to be collected prior to starting treatment (Screening or Visit 2), provided that ECG is normal or has a finding that is not clinically significant.
- e. A pregnancy test will be completed at Week 6, and Week 14/EOS/ET for all females of childbearing potential. Pregnancy tests can be plasma or urine.
- f. Patients receiving valproate or valproic acid will have a blood sample drawn for plasma level of valproic acid. Where possible, effort should be made to get a trough sample. If not, the AED morning dose may be administered prior to the clinic visit. The time of the prior dose of study drug and valproate/valproic acid, if applicable in addition to the time of each blood sample collection will be recorded. During the Treatment Period valproic acid (for patients receiving valproate or valproic acid) blood samples will be taken at Week 6, and Week 14.
- g. On Day 1 the parent/caregiver will be instructed on how to complete the daily skin irritation diary. Scoring of skin irritation will start the evening of Day 1 through discharge from the study by the parent/caregiver. The site will evaluate the parent/caregiver applying the study treatment at each study visit and provide feedback/additional instruction as applicable.
- h. At Weeks 6, and 14 parents/caregivers will administer the dose in the clinic after they have their PK and valproic acid (for patients taking valproate/valproic acid) blood drawn. At Week 14 patients who require a tapering period will be provided a 1 or 2-week supply of study treatment.
- i. A skin assessment examination will be completed by the Investigator at Day 1 pre-dose. Shoulders and upper arms will be examined to determine there are no skin disease or condition, including eczema, psoriasis, melanoma, acne, contact dermatitis, scarring, imperfections, lesions, tattoos, or discoloration that may affect treatment application, application site assessments, or affect absorption of the study drug where study drug could be applied.

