7.1.2. PK Sample Determination of AED Medications

The following data will be summarized separately for each AED medication:

- Plasma concentration occurring at Screening, pre-dose Week 6, 14, and Week 38 EOS/ET.
- Elapsed time between last AED dose and the time of plasma sample collection.

Descriptive statistics (arithmetic mean, median, SD, minimum, maximum, coefficient of variation, geometric mean [plasma concentration]) for the AED plasma trough concentrations and elapse time will be presented at each nominal PK sampling time.

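### The listed AED-level table omits Screening, the only valproate sample before ZYN002; SAP 8.1.11 asks for a Day 1 level that is never drawn; and samples taken after the valproate dose are summarised as troughs

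*SAP*

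**What the plan says.** **Sampling.** Protocol 7.6.20 sets the draws: "At Screening, Week 6, Week 14, and Week 38 EOS/ET Visits, patients will have blood drawn for plasma level of their valproic acid". Protocol 12.1 repeats the four times: valproic acid samples "will be collected at Screening, Week 6, 14, and Week 38 EOS/ET Visits". The Screening schedule has an AED blood sample. The Period 1 schedule (protocol Table 5, SAP Table 4) marks valproate at Weeks 6 and 14 and leaves Day 1 blank. The Period 2 schedule marks Week 38.

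**Timing of the draw.** Protocol 7.6.20 aims for a trough: "All effort should be made to obtain a trough sample for the valproate/valproic acid". Footnote f of the Period 1 schedule and footnote e of the Period 2 schedule ask for a trough where possible and then add: "If not, the AED morning dose may be administered prior to the clinic visit". The time of the last valproate dose and the time of the draw are both recorded.

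**Analysis text.** SAP 7.1.2 lists "Plasma concentration occurring at Screening, pre-dose Week 6, 14, and Week 38 EOS/ET" and, separately, the time elapsed since the last AED dose. It calls the summarised values trough concentrations. Protocol 13.4.2 plans the same for valproic acid. SAP 8.1.11 opens with "Plasma concentration occurring at Day 1", yet its closing sentence presents the statistics at Screening and Weeks 6, 14 and 38. SAP 8.1.12 adds: "Exploratory analyses on the effect of CBD on plasma levels of AEDs, or vice versa, may be explored". It gives no method.

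**Outputs.** SAP section 11 has one AED-level summary, Table 14.3.10: "Summary of Trough Plasma Concentrations for Anti-Epileptic Drugs at each Sampling Time (Weeks 6, 14, and 38"). Listing 16.28 covers the AED blood samples by patient. SAP section 10 identifies no changes from the protocol.

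**The concern.** Safety and tolerability in these children is the primary objective, and valproate levels are collected before and during ZYN002. The natural reading of such data is a comparison with the level before ZYN002. The one table planned for them has no such column, and the SAP text behind it gives the programmer two incompatible sets of time points.

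The label is a separate problem. A value drawn after the morning valproate dose is not a trough. If the share of such values differs between visits, the visit summaries can move although valproate exposure has not changed. They can also stay flat although it has. A reader of a table headed trough concentrations would have no reason to suspect either. What is at stake is how these levels are reported and interpreted.

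**Working it through.** The plan states no figure for AED levels, so there is nothing to reproduce. The check compares the time points and then follows the trough label through.

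**1. Time points side by side**

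| Source | Day 1 | Screening | Weeks 6, 14, 38 |
|---|---|---|---|
| Samples drawn (protocol 7.6.20, 12.1, schedules) | no | yes | yes |
| Protocol 13.4.2 | no | yes | yes |
| SAP 7.1.2 | no | yes | yes |
| SAP 8.1.11, opening bullet | yes | no | no |
| SAP 8.1.11, closing sentence | no | yes | yes |
| Table 14.3.10 title | no | no | yes |

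- Drawn but absent from the table title: Screening.
- Requested but never drawn: Day 1.
- Under the baseline rule in SAP 6.1.2 (last non-missing value before the first dose), the valproate baseline is the Screening value. The table as titled therefore omits the baseline.

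**2. Does pre-dose mean before valproate?** Not necessarily. Footnote h (Period 1) and footnote g (Period 2) have ZYN002 applied in clinic after the blood draw. Footnotes f and e allow the AED dose before the visit. One sample can thus be before the ZYN002 dose and after the valproate dose. SAP 7.1.2 and 8.1.11 contain no rule that excludes or flags it. Elapsed time is summarised as its own variable and does not sort the concentrations.

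**3. Effect of mixing, in symbols.** Let T be the true trough, taken as equal across patients for simplicity. Let r be the ratio of a post-dose level to trough, assumed to exceed 1. Let f be the share of post-dose samples at a visit.

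- Visit mean = T × [1 + f(r − 1)].
- With no true effect, the ratio of the means at visits 2 and 1 = [1 + f₂(r − 1)] / [1 + f₁(r − 1)].
- The ratio is 1 only if f₁ = f₂. If f₂ > f₁ the level appears to rise; if f₂ < f₁ it appears to fall.
- For one patient drawn at trough at Screening and post-dose later, the observed ratio is q × r, where q is the true ratio. With q = 1 the apparent change is r − 1. A true fall is fully hidden when q = 1/r.

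The direction follows from r > 1 alone. The size needs r and f, and the documents give neither.

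**4. How many patients?** About 20 are planned and the number on valproate is not stated. If 5% to 15% of 20 take it (an assumption), 20 × 0.05 = 1 to 20 × 0.15 = 3 patients are expected. Group statistics would be thin with or without the fix, so the within-patient display carries most of the information.

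**The case against.** The best defence is that Screening is planned. The synopsis, protocol 13.4.2, SAP 7.1.2 and the closing sentence of SAP 8.1.11 all require it. SAP section 10 records no departure from the protocol, so the table title looks like an oversight. Trough sampling is the stated aim and post-dose draws are the fallback. Dose and draw times are recorded, elapsed time is summarised at the same visits, and Listing 16.28 gives patient values. With few patients, a reader would turn to the listing anyway. Much of this stands, and it rules out several stronger readings that a reader might infer:

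- *That any change in valproate on ZYN002 cannot be read from this study.* Screening samples exist, the text requires their summary and the listing covers the samples. The defect is a conflict between a title, a bullet and the SAP text.
- *That the defect affects the investigator's review of AED doses in protocol 7.6.20.* That review uses individual valproate levels at visits. It does not use a group table.
- *That the samples were collected to test an interaction.* No objective says so, and SAP 8.1.12 makes the question optional.
- *That a percentage distortion can be stated.* Any such figure would rest on an assumed patient count and an assumed post-dose ratio.

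The promise of a summary for each AED, when on-treatment sampling covers valproic acid only, is a minor wording matter. Protocol 13.4.2 uses it too.

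The defence does not supply a rule for the trough label. A separate summary of elapsed time may alert a careful reader to uneven timing, but it does not take post-dose values out of the trough statistics.

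**Conclusion.** The point holds as a reporting defect with three parts:

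- Table 14.3.10 as titled cannot show change from the level before ZYN002, and it contradicts SAP 7.1.2, the end of SAP 8.1.11 and protocol 13.4.2.
- The Day 1 bullet in SAP 8.1.11 cannot be carried out.
- Samples taken after the valproate dose, which the footnotes allow, enter statistics labelled trough. Uneven draw timing between visits can then suggest a false change or mask a true one.

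The first two parts follow directly from the documents. The third rests only on the assumption that a post-dose level exceeds the trough, and it bites only if the share of post-dose samples differs between visits. Its size cannot be derived from the documents. The correction should be made because it uses only samples and times already collected.

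**What to change.** - **Table 14.3.10:** add Screening as the baseline column beside Weeks 6, 14 and 38.
- **SAP 8.1.11:** replace the Day 1 bullet with the four scheduled times, so that it agrees with its own closing sentence and with 7.1.2.
- **SAP 7.1.2 and 8.1.11:** use the recorded last-dose and draw times to flag each sample as before or after that day's valproate dose. Limit statistics labelled trough to samples taken before it. List the others separately with elapsed time.
- **Patient display:** show each patient's change from Screening at each visit, with elapsed time at both draws.

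The cost is SAP wording and table programming; no new data are needed. The Note to File says that the protocol and SAP will not be updated, so a further note of that kind could carry the change. The downside is fewer values in the trough summary, possibly one or two at a visit. That is a further reason to rely on the patient display.

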11.1. Individual Patient Data Listings

Listing Number	Title	Population
16.1	Listing of Patient Disposition	Enrolled
16.2	Listing of Demographics	Enrolled
16.3	Listing of Baseline Characteristics	Enrolled
16.4	Listing of Medical History	Enrolled
16.5.1	Listing of Prior/Concomitant Medications	Enrolled
16.5.2	Listing of Anti-Epileptic Drugs	Enrolled
16.6.1	Listing of Physical Exam Results	Enrolled
16.6.2	Listing of Neurological Exam Results	Enrolled
16.7	Listing of Protocol Deviations	Enrolled
16.8	Listing of Inclusion and Exclusion	Enrolled
16.9.1	Listing of Urine Drug Screen	Enrolled
16.9.2	Listing of Serum/Urine Pregnancy Results (Female Patients Only)	Enrolled
16.10	Listing of Vital Signs	Enrolled
16.11	Listing of 12-Lead ECG	Enrolled
16.12.1	Listing of Skin Assessment Examination	Enrolled
16.12.2	Listing of Skin Irritation Examination	Enrolled
16.13	Listing of Study Drug Application Record	Enrolled
16.14.1	Listing of Chemistry Labs	Enrolled
16.14.2	Listing of Hematology Labs	Enrolled
16.14.3	Listing of Urinalysis Labs	Enrolled
16.15	Listing of Testosterone Labs (Male Patients Only)	Enrolled
16.16	Listing of Columbia Suicide Severity Rating Scale (CSSRS-Children)	Enrolled
16.17	Listing of Pharmacokinetic Blood Sample Collection Record	Enrolled
16.18.1	Listing of Adverse Events	Enrolled
16.18.2	Listing of Deaths	Enrolled
16.18.3	Listing of Serious Adverse Events	Enrolled
16.18.4	Listing of Adverse Events Leading to Discontinuation	Enrolled
16.18.5	Listing of Patient Skin Irritation from Diary	Enrolled
16.20	Listing of Qualitative Caregiver Reported Behavioral Problems Survey	Enrolled
16.21	Listing of Children's Sleep Habit Questionnaire	Enrolled
16.22	Listing of ABC-C Checklist	Enrolled
16.23	Listing of CGI-S Scale	Enrolled
16.24	Listing of CGI-I Scale	Enrolled
16.25	Listing of PARS-R	Enrolled
16.26	Listing of ADAMS Scale	Enrolled
16.27	Listing of C-SSRS	Enrolled
16.28	Listing of AED Blood Sample	Enrolled

